1.5 Dose Rationale and Risk/Benefits

Based on prior studies in non-lactating women, we plan to administer one spray (4 IU) per nostril 15-30 minutes before NAF collection. The benefits will be greater NAF yield for miR analysis. The risks include rare anaphylactic reactions, common headache, tachycardia or bradycardia, uncommon arrhythmia, very rare hypertension, common nausea and vomiting, rare rash and allergic dermatitis, and uncommon abnormal uterine contractions. Because of the possibility of abnormal uterine contractions, pregnant women will be excluded in the study. [Frequency: *Very common* (> 1/10); *common* (> 1/100 to < 1/10); *uncommon* (> 1/1000 to < 1/100); *rare* (> 1/10 000 to < 1/1000); *very rare* (< 1/10 000), including isolated cases.]

2 Study Objectives

The main objective of this study is to demonstrate the feasibility of characterizing miR profiles in the NAF, serum and tissue of patients with DCIS or invasive breast cancer. Each set of miRs will be assessed for correlation with tumor presence. Tissue and serum are expected to be acquired from all patients. With the addition of intranasal oxytocin, bilateral NAF collection of adequate volume for analysis is expected from 77% of participants at increased risk for breast cancer.¹⁶

Analysis of the miR profiles will include comparisons among the different biological samples (tissue, serum, NAF) in order to understand their relationships with one another. We hypothesize that cancer subtypes will be identifiable by unique miR fingerprints, with the goal of creating a breast cancer screening tool.

²⁸ Pedersen, Cort A., and David L. Penn. "Oxytocin Treatment of Social Cognitive and Functional Deficits in Schizophrenia - Full Text View - ClinicalTrials.gov." *Oxytocin Treatment of Social Cognitive and Functional Deficits in Schizophrenia - Full Text View - ClinicalTrials.gov*. National Institute of Mental Health, n.d. Web. <<http://clinicaltrials.gov/ct2/show/NCT01394471>>.

²⁹ Guastella, Adam J., Stewart L. Einfeld, Kylie M. Gray, Nicole J. Rinehart, Bruce J. Tonge, Timothy J. Lambert, and Ian B. Hickie. "Intranasal Oxytocin Improves Emotion Recognition for Youth with Autism Spectrum Disorders." *Biological Psychiatry* 67.7 (2010): 692-694.

³⁰ Simeon, D., J. Bartz, H. Hamilton, S. Crystal, A. Braun, S. Ketay, and E. Hollander. "Oxytocin Administration Attenuates Stress Reactivity in Borderline Personality Disorder: A Pilot Study." *Psychoneuroendocrinology* 36.9 (2011): 1418-421.

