3.1 General Design

We propose a pilot proof of principle study to assess and compare the miR fingerprint (or profile) in NAF, serum, and tissue from patients undergoing a lumpectomy or mastectomy for in situ or invasive breast cancer. As this study is a proof of concept there is no power presented. Other than the collection of NAF, treatment will not vary from the standard of care. The collection of all specimen types will be completed within the regularly scheduled operative time period. The surgery will not be prolonged in any way for specimen collection. Forty patients (20 with DCIS, 20 with invasive breast cancer) will be entered into the study. A total of 5 patients will also undergo pharmacokinetic (PK) draws during the time of surgery to assess the baseline oxytocin level. All other subjects enrolled will be enrolled into the “non-PK” cohort. Patients receiving care at the Breast Surgery Department at Columbia who meet criteria will be offered participation in the study. Patients will answer a brief questionnaire preoperatively. At the time of surgery patients will undergo a blood draw as well as collection of NAF (via prior administration of intranasal oxytocin, gentle massage, aspirator, and breast pump from both breasts). The NAF and blood samples will be sent to the pathology lab for analysis of miR profile. At the completion of the case, the breast tissue will be sent to pathology per routine. Once in pathology, 5 paraffin-embedded slices will be created to evaluate for miR profile. Serum, NAF, and tissue will be analyzed for their miR profile.

Once total RNA is extracted from the biological samples it will be processed to fluorescently label the microRNAs species according to the V2-Human microRNA array (Agilent). MicroRNA profiling will be obtained and analyzed using the gene-spring software analysis package. First, expression and cluster analysis will be performed to identify the microRNA that are expressed in our samples and to classify them accordingly to their expression. Then, the predicted targets of the over/down-regulated microRNAs will be identified using target prediction bioinformatics tools (TargetScan, Miranda and Pictarvert). Finally, statistical studies between over/under-represented microRNAs will be performed.

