4.1 Inclusion Criteria

Patients meeting the following criteria may be included in the study:

- All female patients with DCIS or invasive breast cancer who are scheduled for a lumpectomy or mastectomy and are receiving surgical care from the Breast Surgery Department at Columbia Medical Center.
- Patients diagnosed with unilateral DCIS or invasive breast cancer

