7.1 Sample Size Consideration

Contralateral breast without disease will serve as the control. In a sample of 40 patients with unilateral disease, we expect 60% of the patients to show significantly altered expression of miRNAs in the diseased breast as compared to the breast without disease for the test to be of clinical relevance. Ideally a detectable difference would be the difference between a null hypothesis of 0% and an alternative of 60% or a second alternative of 35%. Since this study is the first of its kind, we will consider the test to be not clinically relevant if less than 35% of patients show significantly altered expression miRNA in the diseased breast as compared to the breast without disease.

Using a two sample z-test, type I error of 0.05, and a two-sided significance level, a sample size of 40 will have greater than 80% power to detect a difference between a null hypothesis of 35% and an alternative hypothesis of 60%.

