7.2 Statistical Methods

The primary analysis will be conducted to determine the presence and expression levels of 800 miRNA's among DCIS and invasive breast cancer patients. Based on the resulting profiles, we will determine whether or not its expression for each miRNA from the tumor side differs from that of the normal side.

We will interrogate 800 miRNAs. The vast majority will not be expressed in any sample. A minority will be measurable/detectable in some samples and a smaller minority will be detectable in all samples.

The presence of miRNA can be as follows:

- a. Present in tumor and absent in normal
- b. Present in normal and absent in tumor
- c. Present at high level in tumor and low level in normal
- d. Present at high level in normal side and low level in tumor.

Of these a and c are most important and relevant for our analysis. If even a single miRNA is absent in tumor and present in 30% of cancers or if there is at least one miRNA out of these 800 that is present at low levels in all "normals" and high levels in 30% of tumors that would be a "success". We will dichotomize to low and high levels of miRNA to calculate frequencies and the associated risk estimates and 95% confidence intervals. The comparison of proportions will be performed using two-sample z-tests.

CONFIDENTIAL

This material is the property of [name]. Do not disclose or use except as authorized in writing by the study sponsor

7.3 *Subject Population(s) for Analysis*

Patients diagnosed with DCIS or invasive breast cancer.

8 Safety and Adverse Events

8.1 *Definitions*

Adverse Event

An ***adverse event*** (AE) is any symptom, sign, illness or experience that develops or worsens in severity during the course of the study. Intercurrent illnesses or injuries should be regarded as adverse events. Abnormal results of diagnostic procedures are considered to be adverse events if the abnormality:

- results in study withdrawal
- is associated with a serious adverse event
- is associated with clinical signs or symptoms
- leads to additional treatment or to further diagnostic tests
- is considered by the investigator to be of clinical significance

Serious Adverse Event

Adverse events are classified as serious or non-serious. A ***serious adverse event*** is any AE that is:

- fatal
- life-threatening
- requires or prolongs hospital stay
- results in persistent or significant disability or incapacity
- a congenital anomaly or birth defect
- an important medical event

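### Section 7.2 promises unnamed risk estimates, but the one-cancer-breast, one-control-breast design cannot estimate any risk of cancer, and a ratio measure is infinite when the levels success rule is met

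*Combined protocol and SAP*

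**What the plan says.** Section 7.2 (Statistical Methods) states: "We will dichotomize to low and high levels of miRNA to calculate frequencies and the associated risk estimates and 95% confidence intervals". It names no odds ratio, relative risk or risk difference, gives no direction (miRNA level given tumor, or tumor given miRNA level), and gives no method for the intervals. The only comparison method named is the two-sample z-test.

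The design facts that bear on this are:

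- Section 4.1 admits "Patients diagnosed with unilateral DCIS or invasive breast cancer", and section 7.3 defines the analysis population as "Patients diagnosed with DCIS or invasive breast cancer".
- Section 7.1 states: "Contralateral breast without disease will serve as the control".
- Section 3.1 states: "Forty patients (20 with DCIS, 20 with invasive breast cancer) will be entered into the study".
- Section 7.2 counts it as a success if at least one miRNA is "present at low levels in all 'normals' and high levels in 30% of tumors". An alternative branch, joined by *or*, concerns presence: "If even a single miRNA is absent in tumor and present in 30% of cancers". As written, that branch contradicts itself.
- Section 2 places the work in a programme "with the goal of creating a breast cancer screening tool".

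The Study Summary mentions a comparison with a normative reference population. The body of the protocol describes no such sample. It gives no cancer-free women, no follow-up for incident cancer and no disease prevalence.

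**The concern.** A risk estimate in a biomarker study is normally read as a statement about disease: how likely cancer is when the marker is high, or how much likelier than when it is low. Here, among women with usable samples from both sides, half of the breasts are diseased because the design made it so. Any risk computed from those breasts carries that 50% with it.

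The other common reading is an odds ratio or a ratio of frequencies. The levels success rule requires no high normals, which puts a zero in the denominator. The estimate and interval that 7.2 promises would then fail for the very miRNA the study would report as its finding. When no cell is zero, calculating from two side-wise frequencies discards the within-woman pairing.

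At stake is whether the figures published for a candidate miRNA can be computed, and whether a reader planning a screening study could misread them.

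**Working it through.** The plan gives no figure for the risk estimates, so there is none to reproduce on this point. The one computed figure in section 7 is power above 80% for 35% against 60% with 40 patients. It reproduces as a one-sample z-test: Φ((0.25 − 1.96·√(0.35·0.65/40)) / √(0.60·0.40/40)) = 90.6%. A two-sample test with 40 per side gives 61.3%. Nothing below depends on it.

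**Inputs.** 40 women (3.1); one tumor and one control breast each (4.1, 7.1); success pattern 0% of normals and 30% of tumors high (7.2), so 12/40 and 0/40; bilateral NAF adequate for analysis in 77% (section 2), so 0.77 × 40 = 30.8, about 31 pairs.

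**1. Ratio measures at the success pattern.**

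- Unmatched odds ratio: (12 × 40)/(28 × 0) = 480/0.
- Matched odds ratio (discordant pairs): 12/0.
- Ratio of frequencies: 0.30/0.

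All are infinite and none has a Wald interval. Adding 0.5 to each cell gives (12.5 × 40.5)/(28.5 × 0.5) = 35.5, interval 2.0 to 625, which is driven by the correction. An exact lower limit for the matched odds ratio does exist: with p = 0.025^(1/12) = 0.735, it is p/(1 − p) = 2.78. For 10 against 0 in 31 pairs it is 2.24.

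**2. Disease-direction measures.** At the success pattern the relative risk can be computed: (12/12)/(28/68) = 2.43. It is set by the 1:1 sampling. With the same 30% sensitivity and 100% specificity, it would be (0.07 + 0.90)/0.07 = 13.9 at an assumed prevalence of 10%, and (0.007 + 0.99)/0.007 = 142 at 1%.

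An in-sample predictive value moves the other way. Take 12/40 tumors and 1/40 normals high (illustrative; this does not meet the success rule). The in-sample value is 12/13 = 92%. With sensitivity 0.30, specificity 0.975 and prevalence π, PPV = 0.30π/(0.30π + 0.025(1 − π)). That is 1.2% at π = 0.1% and 10.8% at π = 1%. These prevalences are assumptions; the documents give none.

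**3. Pairing away from the zero cell.** Illustrative pairs: 10 both high, 12 tumor only, 2 normal only, 16 neither. The sides are 22/40 = 0.55 and 12/40 = 0.30, difference 0.25.

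- Unpaired: SE = √(0.55·0.45/40 + 0.30·0.70/40) = 0.107; interval 0.04 to 0.46.
- Paired: SE = √(14 − 10²/40)/40 = 0.085; interval 0.08 to 0.42.
- Odds ratios: unmatched (22/18)/(12/28) = 2.85; matched 12/2 = 6.0.

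**4. What remains estimable at the success pattern.**

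| Quantity | 40 pairs (12 v 0) | 31 pairs (10 v 0) |
|---|---|---|
| Tumor side high, exact 95% | 30% (16.6% to 46.5%) | 32% (16.7% to 51.4%) |
| Normal side high, exact upper limit, 1 − 0.025^(1/n) | 8.8% | 11.2% |
| Paired difference, Wald 95% | 0.30 (0.16 to 0.44) | 0.32 (0.16 to 0.49) |

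For 40 pairs the paired SE is √(12 − 12²/40)/40 = 0.072. The unpaired SE, √(0.30·0.70/40), is the same, so at this exact pattern pairing does not change the interval for the difference.

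**The case against.** The strongest reply is that 7.2 goes straight from the risk estimates to a comparison of proportions. It may therefore mean only the proportion high on each side and the difference between them. That reading is plausible and those quantities are fully estimable, including at the success pattern. This stands: the trouble with ratios is conditional on a measure the plan does not name. It does not rescue the sentence, because the plan leaves the measure open and names no paired interval for matched data.

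A second reply also stands: the success rule and the z-test do not use the risk estimate, the study is a proof-of-principle pilot whose primary endpoint is feasibility, and the screening tool is a long-term goal.

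Three narrower replies limit the reach of the point. The 1:1 ratio holds only for women with usable samples from both sides, and the documents do not say that one-sided samples are dropped. The zero cell is forced by the levels branch; the presence branch leads to the same pattern only if absent in normal is assumed to be meant. And the 1:1 design does not by itself rule out an odds ratio: a matched one is estimable when both discordant cells are non-zero.

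A reader might infer that the unmatched odds ratio is a biased version of the matched one. The documents do not support that. One is marginal and the other conditional; they are different estimands, and the gap between 2.85 and 6.0 does not show bias.

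**Conclusion.** The point holds, with limited impact. Under this design no absolute or relative risk of cancer is estimable, whatever miRNA frequencies are observed. If the unnamed measure is an odds ratio or frequency ratio, it is infinite with no Wald interval when the levels success criterion is met; an exact lower limit (2.78 for 12 against 0) still exists. In other patterns, a side-wise two-sample interval ignores the pairing, with an effect of the order of 0.04 to 0.46 against 0.08 to 0.42 in the illustrative table.

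A reader might go further and infer that the reported estimate would be greatly overstated, or that correcting it makes every headline figure less favourable. Neither follows. Overstatement applies only to an in-sample predictive value (92% against 1.2% to 10.8% under assumed prevalences), and no section promises one. The in-sample relative risk of 2.43 is smaller than its value at lower prevalence, and in the illustrative table the matched odds ratio is larger than the unmatched.

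The conclusion assumes that the comparator is the contralateral breast, as 7.1 says, and not the reference population mentioned only in the Study Summary. The 12/40 and 0/40 counts come from the plan's own rule; the other tables are illustrations.

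**What to change.** In section 7.2, replace the risk estimates with the following, for each candidate miRNA:

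1. The tumor-side high frequency and the normal-side low frequency, each with an exact 95% interval and with the number of evaluable breasts stated.
2. The paired difference in proportion high, among women with both sides evaluable, with a named paired 95% interval. A score-type interval is preferable to Wald, whose width collapses to zero when there are no discordant pairs.
3. Optionally, the matched odds ratio with exact limits, reported as a lower limit only when the normal-only cell is zero.

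Add one sentence stating that no absolute or relative risk of cancer is estimated. If the normative reference population in the Study Summary is still intended, describe it; otherwise remove it.

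The cost is a wording change and a few lines of analysis code. No new patients, samples or assays are needed.

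### Section 7.2 needs absent, low and high to describe its patterns and success rule, but the only coding it states is low/high, and no single two-level code serves both parts of that rule

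*Combined protocol and SAP*

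**What the plan says.** Section 7.2 lists four tumor/normal patterns. Pattern a is "Present in tumor and absent in normal", and b is its mirror image. Pattern c is "Present at high level in tumor and low level in normal", and d is its mirror image. In c and d, low is a level of a miRNA that is present, so the list implies three states per breast: absent, present-low and present-high. On priority the section says "Of these a and c are most important and relevant for our analysis".

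The success rule has two parts. The first concerns presence: "If even a single miRNA is absent in tumor and present in 30% of cancers". The second concerns level: "present at low levels in all 'normals' and high levels in 30% of tumors".

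The section then states its one coding rule: "We will dichotomize to low and high levels of miRNA to calculate frequencies and the associated risk estimates and 95% confidence intervals". Proportions are to be compared with two-sample z-tests. Section 7.2 gives no detection limit, no low/high cut-off and no rule for coding an absent result. The Study Summary mentions calculating the presence of miRs but gives no coding rule either.

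**The concern.** The patterns and the success rule need three states, while the stated coding has two. Depending on where absent results go, some tumor/normal differences that 7.2 singles out as most relevant may be recorded as no difference, merged with another pattern, or dropped.

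Absent results will not be rare. Of the 800 miRNAs the section says "The vast majority will not be expressed in any sample", and of the rest "A minority will be measurable/detectable in some samples and a smaller minority will be detectable in all samples". Informative miRNAs will therefore often have absent calls in some samples.

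The plan also declares success if a single miRNA meets either part of the rule. If the handling of absent results is settled only once the data are in hand, that choice could decide whether the study is called a success.

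**Working it through.** The plan states no figure for this point, so there is none to reproduce. The check has two steps.

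**Step 1: try each possible two-level code.** Three states on each side give 3 × 3 = 9 tumor/normal combinations. The three that make up patterns a and c are:

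| Tumor / normal | Pattern | Absent coded low | Absent treated as missing | Cut placed at detection |
|---|---|---|---|---|
| low / absent | a | low/low: no difference | pair dropped | difference kept |
| high / absent | a | high/low: same as c | pair dropped | difference kept |
| high / low | c | high/low: kept | high/low: kept | both above the cut: no difference |

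Patterns b and d behave as mirror images. Low/low and high/high show no difference under every code. Absent/absent shows no difference, or is dropped if absent is missing.

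Each column loses something. The first loses part of pattern a and cannot separate the remainder from c. The second loses all of a. The third loses all of c, and it also conflicts with the section's own use of low as a level of a present miRNA. Moving the low/high cut anywhere above the detection limit does not recover the low/absent pair.

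**Step 2: size, with absent coded low.** Inputs:

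- 40 pairs (7.1).
- Pattern a in 30% of pairs, the threshold in 7.2: 0.30 × 40 = 12.
- The share of those 12 tumors at low level is an assumption, shown over its full range, because the documents do not give it.
- No normal breast is high, so the normal-side count is 0 of 40.

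The counted pairs are k = 12 × (1 − share low). The plan's test, in its pooled form, is z = (k/40) / √[p̄(1 − p̄) × 2/40], with p̄ = k/80. For k = 6: p̄ = 0.075, z = 0.15 / √(0.075 × 0.925 × 0.05) = 0.15 / 0.0589 = 2.55, two-sided p = 0.011.

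| Share of pattern-a tumors at low level | Counted pairs | Frequency | z | Two-sided p |
|---|---|---|---|---|
| 0% | 12 | 30% | 3.76 | 0.0002 |
| 25% | 9 | 22.5% | 3.18 | 0.0015 |
| 50% | 6 | 15% | 2.55 | 0.011 |
| 75% | 3 | 7.5% | 1.77 | 0.077 |
| 100% | 0 | 0% | 0 | 1 |

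These p-values are for one miRNA, before any correction for multiple testing. The two-sample z-test is used because the plan names it; whether it suits paired breasts is a separate matter.

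If absent is treated as missing, all 12 pairs drop out, at most 28 of 40 remain, and the pattern-a count is 0 whatever the levels. A detected yes/no variable gives 12/40 = 30% in every row.

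**The case against.** The strongest reply is that the text does not say every frequency will use the low/high code. Section 7.2 opens by saying the primary analysis covers presence as well as expression level. The Study Summary also lists a calculation of presence. The first part of the success rule, though garbled, mentions neither low nor high. The dichotomizing sentence follows directly on the second part and can be read as applying to levels only. On that reading pattern a is counted by presence and nothing is lost. This stands as far as it goes: a presence count is implied. But no method for it is given, and the only coding rule written down does not provide one.

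Several stronger conclusions are tempting and are not supported:

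- A reader might infer that pattern a is certain to be miscounted. It is not. If absent is coded low and every pattern-a tumor is high, the combined a and c count is unchanged, and only the distinction between a and c is lost.
- A reader might infer that pattern a is the plan's leading marker. The section ranks a and c jointly; order in a lettered list is not a ranking.
- A reader might infer from the frequency of absent results that pattern a is common. The detectability sentences concern samples in general, not tumor-present/normal-absent pairs, and absence on both sides creates no difference to lose.

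It can also be said that this is a pilot whose primary endpoint (3.2) is feasible miR analysis, and that the array values can be recoded later. That limits the harm. It does not remove the risk of choosing the coding after seeing the data.

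**Conclusion.** The inconsistency stands. Section 7.2 implies three states and sets a two-part success rule, one part on presence and one on level. Its only stated coding for frequencies, risk estimates and confidence intervals has two levels, and no single two-level code can serve both parts.

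The size is not fixed by the documents. With 12 of 40 pattern-a pairs and absent coded low, the loss runs from none (0% at low level) to all 12 (100%). If the low/high count were used to judge the 30% mark, the frequency would already be below it at 25% low (22.5%). The unadjusted z-test would cross 0.05 between 50% and 75% low (p = 0.011 and 0.077). These figures rest on the assumed low-level shares and on no normal breast being high.

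This should be changed before analysis. It is a gap in the written rule that can lose information, not proof that information will be lost.

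**What to change.** Replace the dichotomizing sentence in 7.2 with two prespecified binary variables per breast and miRNA:

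1. **Detected yes/no**, with the detection limit stated.
2. **High yes/no**, with the cut-off stated and an absent result counted as not high.

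Define both on evaluable samples from both breasts, so that absent is a measured result and not a failed or missing sample. Use the first variable to count pattern a for the first part of the success rule, and the second to count pattern c for the second part. Report frequencies and intervals for each. Because both variables are recorded, a tumor-high/normal-absent pair remains identifiable; state whether it also counts toward the second part. A combined tumor-higher count on the ordered scale absent < low < high can be added, but should not replace the two separate counts, since the success rule has two separate parts.

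In the same edit, correct the first part of the rule. As written it requires the miRNA to be absent in the tumor and present in cancers, which contradicts itself; it should agree with pattern a.

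The cost is about one paragraph in 7.2 and one further coded variable from array data the study already produces. The drawbacks are that calls near the detection limit are noisier and that there are two sets of frequencies to report instead of one.

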Statistical Methodology	Calculation of presence of miRs compared to normative reference population, binomial test to determine significant differences, Benjamin Hochberg procedure to rule out false positives, and ranking of miRs by p-value to determine most favorable biomarkers.

CONFIDENTIAL

This material is the property of [name]. Do not disclose or use except as authorized in writing by the study sponsor

1 Introduction

This document is a protocol for a human research study. This study is to be conducted according to US and international standards of Good Clinical Practice (FDA Title 21 part 312 and International Conference on Harmonization guidelines), applicable government regulations and Institutional research policies and procedures.

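### miRNAs singled out as the best of 800 will carry inflated tumor-minus-normal estimates and 95% intervals that cover below 95%, because the same women supply both selection and estimation

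*Combined protocol and SAP*

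**What the plan says.** Section 7.2 states "We will interrogate 800 miRNAs" and adds "The vast majority will not be expressed in any sample", without saying how many are expected to be detectable. Levels are to be split into high and low in order to "calculate frequencies and the associated risk estimates and 95% confidence intervals", and tumor and normal sides are compared with two-sample z-tests.

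Two selection steps appear. In Section 7.2, one miRNA out of the 800 is enough for success, for example one that is low in every normal breast and shows "high levels in 30% of tumors that would be a" success. In the Study Summary (Statistical Methodology), the plan lists "Benjamin Hochberg procedure to rule out false positives" and then "ranking of miRs by p-value to determine most favorable biomarkers".

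The data come from a single cohort. Section 3.1 says "Forty patients (20 with DCIS, 20 with invasive breast cancer) will be entered into the study", and Section 2 says "bilateral NAF collection of adequate volume for analysis is expected from 77% of participants at increased risk for breast cancer". No hold-out set, cross-validation, shrinkage, selection-adjusted interval or named confirmation cohort is described.

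**The concern.** An ordinary 95% interval is calibrated for an miRNA chosen before the data are seen. When the miRNA is chosen because its observed difference is the most extreme of many, that difference is partly signal and partly favorable chance. The estimate is then too large on average, and its interval is centered in the wrong place.

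Section 2 gives a breast cancer screening tool as the eventual goal and describes the project as a foundation for later miR work. The highlighted miRNAs and their tumor and normal frequencies are what a later team would naturally carry forward. If those figures are inflated, weak candidates look strong, and a later study planned on them would be too small.

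**Working it through.** **The plan's own figure.** The plan gives no figure for bias or coverage. Its only operating characteristic is power above 80% for 35% versus 60% with 40 women (Section 7.1). A one-sample z-test reproduces it: standard errors are √(0.35×0.65/40) = 0.0754 and √(0.60×0.40/40) = 0.0775, and (0.25 − 1.96×0.0754)/0.0775 = 1.32, which gives about 90.6%. This concerns a single proportion and says nothing about estimates after a search.

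**Inputs from the documents.** 800 candidates; 40 women; 77% with adequate bilateral fluid, so 0.77×40 = 30.8, about 31; two-sample z-test; two-sided 0.05.

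**Assumptions.** Number detectable (30, 100 or 800), high-level frequencies, share truly altered, independence between miRNAs and between breasts, and a 5% Benjamini-Hochberg level.

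**Method.** In each simulated trial:

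1. Draw high-level counts x (tumor) and y (normal) for each miRNA.
2. Compute z = (x/n − y/n)/√(2p(1−p)/n), with p = (x+y)/(2n).
3. Take the miRNA with the most extreme z.
4. Compute its difference and ordinary 95% interval in the same women, and compare them with its true difference.

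**Setting A: 31 pairs, 100 detectable miRNAs, non-markers high in 30% on both sides.**

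| True markers | Mean top estimate | Mean truth | Coverage |
|---|---|---|---|
| None | 0.29 | 0 | 5% |
| Ten, 35% vs 15% | 0.36 | 0.18 | 64% |
| Five, 50% vs 10% | 0.52 | 0.40 | 86% |

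Repeat runs gave coverage of 4–5%, 60–64% and 81–87%.

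**Setting B: 40 women, 30 / 100 / 800 detectable miRNAs, Newcombe intervals.**

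| True markers | Estimate | Truth | Coverage |
|---|---|---|---|
| None (both sides 50%) | 0.26 / 0.31 / 0.37 | 0 | 17% / 0.3% / 0% |
| 10% of miRNAs, 60% vs 35% | 0.35 / 0.42 / 0.51 | 0.21 / 0.23 / 0.25 | 77% / 72% / 15% |
| One, 30% vs 2% | 0.29 / 0.31 / 0.35 | 0.25 / 0.23 / 0.15 | 89% / 78% / 53% |
| One dominant, 60% vs 5% | 0.55 | 0.54–0.55 | about 96% |

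Without selection, coverage is 94–95%.

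**Does Benjamini-Hochberg repair it?** In the second row of setting B, restricted to trials that pass at 5%, the estimates are 0.41 / 0.44 / 0.51 against truths of 0.24 / 0.24 / 0.25, with coverage of 79% / 68% / 15%. The inflation remains.

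**The success rule as a selector.** Read as an observed share with 40 women, it needs at least 0.30×40 = 12 high tumors and no high normals. Any miRNA highlighted by it therefore shows a difference of at least 12/40 − 0/40 = 0.30, whatever its true difference. With 31 women, 0.30×31 = 9.3, so at least 10/31 = 0.32.

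**Check of the remedies.** Intervals at Bonferroni width covered 95–99% in setting A and about 94–99% in the first two scenarios of setting B. Repeating the whole procedure with one woman left out at a time gave 0.01 / 0.17 / 0.40 in setting A, against truths of 0 / 0.18 / 0.40, with a standard deviation of about 0.20–0.27. A percentile bootstrap of the selected difference covered only 0%, 0% and 21%.

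**The case against.** Several objections have force.

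- **The link between ranking and intervals is not explicit.** Section 7.2 compares sides for every miRNA and does not limit intervals to top-ranked ones. Ranking stands only in the Study Summary, which uses a binomial test against a normative reference rather than a two-sample z-test against the other breast. This stands in part. The fault arises when miRNAs are highlighted, and a reader who inferred that every interval in the study is invalid would go too far. But the success rule in Section 7.2 selects on the same data without any ranking.
- **The no-marker case skips the plan's own filter.** With no true marker, Benjamini-Hochberg at 5% passes anything in only about 5% of trials. This stands, so the 5% coverage figure is an extreme. The settings with real markers carry the point.
- **A reader might infer that the success rule is easily met by chance.** That would count tumors only and omit the condition on normals. If 100 detectable miRNAs are each high in 15% of tumors in 40 women, the chance that at least one meets both conditions is 55%, 14% or 0.2% when normals are high in 1%, 5% or 15%. The documents do not support a general claim.
- **The leave-one-out estimate is noisy.** Its root mean squared error exceeded that of the naive estimate in both real-marker settings (0.23 vs 0.21, and 0.20 vs 0.14). It also scores a procedure whose pick may change between folds. This stands and shapes the fix.
- **This is a feasibility pilot.** The primary endpoint is feasible miR analysis, and no text says a later study will be sized on these estimates. That consequence is inferred. It lowers the urgency but does not make the intervals correct.

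**Conclusion.** The concern holds for miRNAs highlighted as best or as meeting the success rule: their tumor-minus-normal estimates are inflated and their ordinary 95% intervals cover below 95%. A reader might infer that the intervals never cover. The results do not support that: coverage ran from about 5% to 86% with 31 pairs and 100 independent detectable miRNAs, was near nominal with one dominant marker, and was 94–95% for miRNAs not selected. The size depends on the number detectable, the true frequencies and independence, none of which the plan gives. Correlation between miRNAs would change the size but not the mechanism. A high/low cut-off chosen from the data would add further optimism. The plan should be changed on this point; the feasibility endpoint is not affected.

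**What to change.** In Section 7.2, and in the Study Summary to match:

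1. **Intervals.** For miRNAs highlighted as best or as meeting the success rule, replace ordinary 95% intervals with selection-adjusted ones. Use either Bonferroni width over the m detectable miRNAs (level 1 − 0.05/m each) or false-coverage-rate intervals matched to the Benjamini-Hochberg step (level 1 − R×0.05/m for R selected miRNAs, with 5% assumed). Define detectable in advance, without reference to which side is tumor. The false-coverage-rate form was not simulated here.
2. **Estimates.** Beside the naive estimate, report a leave-one-woman-out estimate that repeats cut-off, test and ranking with both breasts of the woman left out together. Describe it as the performance of the selection procedure, not of a named miRNA. Adjusted intervals alone do not remove the inflation of the point estimate.
3. **Labels.** Mark unadjusted figures as exploratory and not corrected for selection.
4. **Bootstrap.** Do not specify a bootstrap of the selected difference.

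The cost is a few lines of wording and code, with no added patients, visits or assays. Highlighted intervals become wider: with m = 100 the normal multiplier rises from 1.96 to 3.48, a factor of 3.48/1.96 = 1.78. Effect sizes will look less favorable, and the leave-one-out estimate will be imprecise.
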